1.2. Trial Design

A target of 450 adult male and female participants, 18 to 65 years of age (inclusive), will be randomized in a 2:2:2:2:1:1 ratio to one of the following intervention arms:

• Arm 1:	JNJ-3989 (100 mg) +	JNJ-6379 (250 mg qd) +	NA	(N=90)
• Arm 2:	JNJ-3989 (200 mg) +	Placebo +	NA	(N=90)
• Arm 3:	JNJ-3989 (100 mg) +	Placebo +	NA	(N=90)
• Arm 4:	JNJ-3989 (40 mg) +	Placebo +	NA	(N=90)
• Arm 5:	Placebo +	JNJ-6379 (250 mg qd) +	NA	(N=45)
• Arm 6 (control):	Placebo +	Placebo +	NA	(N=45)

NA treatment refers to entecavir (ETV), or tenofovir disoproxil fumarate (TDF), or tenofovir alafenamide (TAF). Treatment duration with JNJ-3989/placebo and/or JNJ-6379/placebo is of 48 weeks. Participants who meet the NA treatment completion criteria at Week 48 will also stop NA treatment and be monitored closely during the follow-up phase. NA treatment may be re-started at any time if protocol-defined NA re-treatment criteria will be met.

The study will be conducted in the following phases:

- Screening phase:** 4 weeks. If necessary, eg, for operational reasons, the screening phase may be extended up to a maximum of 6 weeks on a case-by-case basis and in agreement with the sponsor.
- Double-blind study intervention phase:** from Day 1 (ie, baseline) up to Week 48.
- Follow-up phase:** for 48 weeks after the end of investigational intervention. For participants who complete NA treatment during follow-up, the follow-up phase will be extended to 48 weeks after the end of NA treatment. The follow-up phase has a maximum duration of 96 weeks.

Participants will be considered to have completed the study if they have completed the assessments of the end of study visit ([Extended] Follow-up Week 48).

An Independent Data Monitoring Committee (IDMC) was commissioned for this study to monitor and review data in an unblinded manner on a regular basis to ensure the continuing safety of the study participants. The committee will meet periodically to review unblinded data, as well as the results from the interim analyses (IAs) at prespecified time points (see Section 3). A separate IDMC SAP describes details of the safety and efficacy analyses included in the IDMC periodical data reviews.

In addition, an independent Flare Expert Panel (iFLEP) was appointed for flares monitoring and adjudication. Details on the IDMC and iFLEP activities are described in their respective charter.

1.3. Statistical Hypotheses for Trial Objectives

Based on the primary efficacy endpoint, the proportion of participants meeting the NA treatment completion criteria at Week 48, the primary hypotheses are as follows:

- Any of the combination regimens is more efficacious than NA treatment alone.
 - There is a positive dose-response signal across the 3 doses of JNJ-3989 (40, 100, and 200 mg) on the background of NA compared with NA treatment alone.
 - One or both combination regimens JNJ-3989+JNJ-6379+NA and JNJ-6379+NA are more efficacious than NA treatment alone.
- The combination regimen of JNJ-3989 (100 mg)+JNJ-6379+NA is more efficacious than JNJ-3989 (100 mg)+NA and/or JNJ-6379+NA regimens.

1.4. Sample Size Justification

The total study sample size is 450 participants with a 2:2:2:2:1:1 randomization ratio, where 90 participants will be randomly allocated to each of the arms including a JNJ-3989 dose (Arms 1 to 4) and 45 participants will be randomly assigned to each of the arms with no JNJ-3989 component (Arms 5 and 6). Due to the global impact of the pandemic Coronavirus Disease 2019 (COVID-19) and the use of the modified ITT analysis set as primary set for the efficacy analyses, study enrollment was extended by approximately 5% of participants.

Statistical power to test a dose-response signal (max trend test) was assessed using the generalized version of the MCP-Mod ([Pinheiro J. et al., 2014](#)) applied to the binary primary efficacy endpoint on the logit scale using data from Arms 2, 3, and 4 (JNJ-3989 at 200, 100, and 40 mg dose, respectively +NA), and Arm 6 (placebo+placebo+NA) as control. The “max trend test” is to test the null hypothesis that none of the doses is better than control (i.e. the flat dose response curve). The power to reject the null hypothesis is $\geq 85\%$ under all 5 candidate dose-response models for an absolute response rate of the highest dose of JNJ-3989 of at least 25% (one-sided alpha level of 5%). In addition, assuming a response rate of 5% in control Arm 6, the study sample size provides a statistical power $\geq 84\%$ to detect a difference of $\geq 20\%$ in the primary endpoint between Arm 1 and Arm 6, and power $\geq 76\%$ for at least a 20% delta between Arm 5 and Arm 6, using a fixed sequence approach for controlling for multiplicity.

The testing among the regimens (Arm 1, 3, and 5) will be performed using the min test approach control for the one-sided Type 1 error of 0.05. The chosen study sample size and randomization allocation provides acceptable power levels also for the comparison of different combination regimens, ie, JNJ-3989+JNJ-6379+NA (Arm 1, 100-mg dose of JNJ-3989) versus JNJ-3989+NA (Arm 3, 100-mg dose of JNJ-3989), and versus JNJ-6379+NA (Arm 5), respectively. For example, for the same delta of 25% between Arm 1 and Arm 3 and between Arm 1 and Arm 5, the power to conclude that Arm 1 is statistically superior to Arm 3 and Arm 5 is 87%, assuming a response rate of 25% in both Arm 3 and 5. Details are provided in Section 9 of the protocol Amendment 1.

1.5. Randomization and Blinding

Randomization

Central randomization is implemented in this study. Participants are randomly assigned to 1 of 6 intervention arms with a ratio of 2:2:2:2:1:1 (Arms 1:2:3:4:5:6). The randomization is stratified by HBeAg status at screening (positive versus negative) and by treatment history (not currently treated versus virologically suppressed).

Blinding

At Week 48 or earlier at the time of treatment discontinuation, it will be communicated to the investigators whether the participants were allocated to either an intervention arm (Arms 1 to 5) or the control arm (Arm 6) to determine which follow-up visit schedule will be followed. Only at Week 72, randomization codes (for Arms 1 to 5) will be fully disclosed to the investigators. The sponsor will be fully unblinded at the time of the primary analysis (all participants have completed Week 48 or discontinued early).

Sponsor personnel involved in the pharmacokinetic and pharmacodynamic modelling will have access to the pharmacokinetic and pharmacodynamic data before formal unblinding for the primary analysis. Sponsor personnel involved in trial conduct, data management, and statistics will not have access to these data prior to the primary analysis. The sponsor will be fully unblinded at the time of the primary analysis which will be conducted at the time when all participants have completed Week 48 or discontinued earlier.

2. GENERAL ANALYSIS DEFINITIONS

The SAP will use throughout the document the following definitions:

- *Study treatment* refers to: JNJ-3989, JNJ-6379, placebo and NA (ETV, TDF, or TAF)
- *Study agent* refers to: JNJ-3989, JNJ-6379, or placebo
- *Study intervention arm* refers to:
 - Arm 1: JNJ-3989 (100 mg) + JNJ-6379 (250mg qd) + NA
 - Arm 2: JNJ-3989 (200 mg) + placebo + NA
 - Arm 3: JNJ-3989 (100 mg) + placebo + NA
 - Arm 4: JNJ-3989 (40 mg) + placebo + NA

Arm 5: placebo + JNJ-6379 (250mg qd) + NA

Arm 6: placebo + placebo + NA

2.1. Analysis Phases and Visit Windows

2.1.1. Analysis Phase

The analysis phases are defined in [Table 1](#) below.

Table 1: Analysis Phases Start and End Dates

Analysis phase	Start date	End date
Screening	The date of signing the informed consent	1 day before the first study agent intake
Double-blind Study intervention	Date of first study agent intake	The maximum of last intake of JNJ-3989/placebo, last intake of JNJ-6379/placebo and Week 48 date + 5 days or cut-off date*, whichever comes first
Follow-up	End of the double-blind study intervention phase + 1 day	If the participant stops NA treatment at/up to Week 48, study termination date (date of last contact) or cut-off date*, whichever comes first
		If the participant completes NA treatment post Week 48 during the follow-up phase, (date of the last NA intake + 5 days) or cut-off date*, whichever comes first
		If the participant never completes NA treatment during follow-up phase, trial termination date (date of last contact) or cut-off date*, whichever comes first
Extended Follow-up #	End of the follow-up phase + 1 day	Trial termination date (date of last contact) or cut-off date*, whichever comes first

Note: +5 days is only attributed to adverse events and concomitant medications.

*Cutoff dates will be defined to match the prespecified timepoints for IDMC safety monitoring, interim analysis and the primary analysis, respectively.

The extended follow-up phase is only for the participants who completed the NA treatment during the follow-up phase

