2.1.2.3. Extended Follow Up Relative Day

Extended Follow Up (EFU) start date (EFU Day 1) is defined in [Table 1](#). All efficacy and safety assessments during the extended FU phase will be assigned a day relative to this date. The EFU study day in the extended FU treatment phase (ADY) is defined as:

$$EFU\ ADY = visit\ date - EFU\ start\ date + 1$$

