2.1.3. Analysis Visits and Time Points

All visits for all assessments (safety, efficacy or PK) will be uniquely allocated within each phase to an analysis time point based on the analysis relative day (ADY) compared with the target day based on [Table 2](#). All assignments will be made in chronological order. Once a visit is assigned to a visit window (Time interval in [Table 2](#)), it will no longer be used for a later time point except for the end of treatment (EOT) and the end of study (EOS) visits. If two or more visits fall within the same interval in the same phase, only one measurement will be selected for the analysis time point per phase in order to have only one evaluation per participant. The following rules will be applied:

1. The measurement closest to the target day in that phase will be used.
2. If the measurements fall equidistant from the target day, the last measurement in chronological order within the interval will be used per phase
3. If there are two or more measurements on the same day, then the last measurement in chronological order will be used. If the time of the assessment is not available the highest record/sequence number will be selected.

The listings will include all measurements, also those multiple assessments within the same visit window/phase.

End of treatment (i.e. EOT) and end of study (i.e. EOS) time points will be included in all analysis over time unless stated otherwise.

Note: For the selection of the patient-reported outcome (PRO) measurements the above algorithm needs to be performed on the entire questionnaire (filled in at a specific date and time) and not on the individual questions /items (i.e., not mixing answers from different questionnaires)

Table 2 provides the analysis time points, time intervals for each visit per analysis phase.

Table 2: Analysis Time Points and Time Intervals by Analysis Phase

a) **Screening and Double-Blind Phases**

Analysis phase	Target day	Analysis time point (Week)	Analysis time point (label)	Time interval (days)
Screening	$-\infty$	-1	Screening	<0
Double-Blind	1	0	Baseline	Pre-dose
	8	1	Week 1	[2,11]
	15	2	Week 2	[12,22]
	29	4	Week 4	[23,36]
	43	6	Week 6	[37,50]
	57	8	Week 8	[51, 71]
	85	12	Week 12	[72, 99]
	113	16	Week 16	[100, 127]
	141	20	Week 20	[128, 155]
	169	24	Week 24	[156, 183]
	197	28	Week 28	[184, 211]
	225	32	Week 32	[212, 239]
	253	36	Week 36	[240, 267]
	281	40	Week 40	[268, 295]
	309	44	Week 44	[296, 323]
	337	48	Week 48	[324,350]

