	last visit in double-blind phase	49 ^a	EOT ^a	

^a End of treatment (EOT) visit will be the last post-baseline visit in double-blind phase.

b) **Follow-Up Phase**

Analysis phase (FU)	Target day	Analysis time point (Week)	Analysis time point (label)	Time interval (days) ^a (Arm 1-5 and Arm 6 [NA stopped])	Time interval (days) ^a (Arm 6 [NA continued])
Follow-up ^a	15	50	Follow-up Week 2	[1, 22]	
	29	52	Follow-up Week 4	[23,36]	
	43	54	Follow-up Week 6	[37,50]	
	57	56	Follow-up Week 8	[51, 71]	
	85	60	Follow-up Week 12	[72, 99]	[1, 99]
	113	64	Follow-up Week 16	[100, 127]	
	141	68	Follow-up Week 20	[128, 155]	
	169	72	Follow-up Week 24	[156, 190]	[100, 190]
	197	76	Follow-up Week 28	[191, 204]	
	211	78	Follow-up Week 30	[205, 218]	
	225	80	Follow-up Week 32	[219, 232]	
	253	84	Follow-up Week 36	[233, 274]	[191, 274]
	281	88	Follow-up Week 40	[275, 288]	
	295	90	Follow-up Week 42	[289, 302]	
	309	92	Follow-up Week 44	[303, 316]	
	337	96	Follow-up Week 48	[317, $+\infty$]	[275, $+\infty$]

c) Extended Follow-Up Phase

Analysis phase (EFU)	Target day	Analysis time point (Week)	Analysis time point (label)	Time interval (days) ^a
Extended Follow-up	15	102	Ext Follow-up Week 2	[1, 22]
	29	104	Ext Follow-up Week 4	[23, 36]
	43	106	Ext Follow-up Week 6	[37, 50]
	57	108	Ext Follow-up Week 8	[51, 71]
	85	112	Ext Follow-up Week 12	[72, 99]
	113	116	Ext Follow-up Week 16	[100, 127]
	141	120	Ext Follow-up Week 20	[128, 155]
	169	124	Ext Follow-up Week 24	[156, 190]
	197	128	Ext Follow-up Week 28	[191, 204]
	211	130	Ext Follow-up Week 30	[205, 218]
	225	132	Ext Follow-up Week 32	[219, 232]
	253	136	Ext Follow-up Week 36	[233, 274]
	281	140	Ext Follow-up Week 40	[275, 288]
	295	142	Ext Follow-up Week 42	[289, 302]
	309	144	Ext Follow-up Week 44	[303, 316]
	337	148	Ext Follow-up Week 48	[317, +∞]
	last visit in the study	999 ^a	EOS ^a	

^a End of study (EOS) visit (last available data during the extended follow-up) will be the last visit in the study.

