3.1. Interim Analyses

The primary analysis will be conducted at the time when all participants have completed Week 48 or discontinued earlier.

Interim analyses will be conducted to monitor safety and evaluate the time course of different disease markers to support the sponsor's internal decision-making, interactions with health

authorities, as well as inform decisions about additional studies and/or investigation of other treatment combinations. Three IAs are planned when:

- All participants have completed Week 60 visit or discontinued earlier.
- All participants have completed Week 72 visit or discontinued earlier.
- All participants have completed Week 96 visit or discontinued earlier.

One additional IA may be performed at the sponsor's discretion when all participants, who completed NA treatment at Week 48 of follow-up, have completed Week 120, i.e. Week 24 of the extended follow-up, or discontinued earlier. As all IAs follow the primary analysis, they will be conducted by the sponsor. Both primary and interim analyses will be based on all data available at the predefined cut-off time, including data at later time points for those participants who have reached subsequent visits

The final analysis will be performed when all participants have completed the last study visit or discontinued earlier.

This SAP covers the definitions of analysis sets, derived variables and statistical methods for the primary, interim and final analyses of this study.

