5.4.5.2. HBsAg Thresholds

The following cut-offs for HBsAg values and decreases from baseline will be used in separate summaries over time by intervention arm. The number and proportion of participants who meet those HBsAg thresholds during the study will be summarized descriptively by intervention arm and analysis phase over time.

Thresholds for **HBsAg values**:

- <1000 IU/mL
- <100 IU/mL
- <10 IU/mL
- <1 IU/mL
- <0.05 IU/mL

Thresholds for **HBsAg decreases from baseline**:

- $\geq 0.3 \log_{10}$ IU/mL
- $\geq 0.5 \log_{10}$ IU/mL
- $\geq 1 \log_{10}$ IU/mL
- $\geq 2 \log_{10}$ IU/mL
- $\geq 3 \log_{10}$ IU/mL
- $\geq 4 \log_{10}$ IU/mL

Cumulative percentage of participants achieving any given decrease from baseline in HBsAg at Week 72 and at Week 96, separately, will be presented graphically.

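### Participants who stop NA during follow-up move to a restarted time axis, so responders lose their Week 96, and often Week 72, values in the by-week marker outputs; extended-visit week labels are also inconsistent

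*SAP*

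**What the plan says.** SAP Table 1 (2.1.1) gives the FU phase three possible ends. For late completers it is "If the participant completes NA treatment post Week 48 during the follow-up phase, (date of the last NA intake + 5 days" or the data cut-off, whichever is earlier. A footnote limits the extension: "5 days is only attributed to adverse events and concomitant medications". For efficacy data, the phase therefore ends at the last NA intake. By contrast, "If the participant stops NA treatment at/up to Week 48, study termination date (date of last contact" applies to those who stop by Week 48, and those who never stop also stay in FU to the end of the trial.

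Extended follow-up starts the next day, and SAP 2.1.2.3 restarts the count: "All efficacy and safety assessments during the extended FU phase will be assigned a day relative to this date". SAP 2.1.3 says that visits "will be uniquely allocated within each phase to an analysis time point based on the analysis relative day (ADY". Analysis Weeks 72 and 96 appear only in the FU table (2b). Extended visits receive Weeks 102 to 148 (2c).

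SAP 5.4.5.2 reads HBsAg at fixed study weeks: "Cumulative percentage of participants achieving any given decrease from baseline in HBsAg at Week 72 and at Week 96, separately, will be presented graphically". Sections 5.4.5.3 and 5.4.5.4 do the same for HBeAg and HBV DNA, and the mixed model for repeated measures (MMRM) in 5.4.5.1 uses analysis week as its time factor.

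SAP 3.1 refers to participants who "have completed Week 120, i.e. Week 24 of the extended follow-up". Table 2c gives the row "Ext Follow-up Week 24" the value 124.

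**The concern.** The move off the FU axis is caused by response. Under protocol 6.6 a participant stops NA in follow-up only after meeting the ALT, HBV DNA, HBeAg and HBsAg (<10 IU/mL) criteria together. Non-completers and Week 48 completers keep their Week 72 and Week 96 slots, while late completers can lose one or both. If they still have low HBsAg at those weeks, the observed results understate HBsAg control most in the arms with the most late responders. The Week 72 and Week 96 interim analyses are meant partly to show the time course of these markers for sponsor decisions and health-authority discussions.

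The label conflict is a second, smaller matter. A programmer working from Table 2c and one working from SAP 3.1 would select different visits as Week 120.

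**Working it through.** **Inputs.** FU windows for Arms 1–5 (SAP Table 2b): Week 72 = FU days 156–190; Week 96 = FU day 317 onward. Arms 1–5 visits while on NA (protocol 1.3.2): FU W2, 4, 6, 8, 12, 16, 20, 24, 30, 36, 42, 48, each ±4 days. Stop rule (protocol 6.6): the next scheduled visit after a qualifying lab taken at or before FU W42 (FU W36 for Arm 6). Assumption: the last NA dose is taken on the day of the stop visit.

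**Step 1: reproduce the labels.** Table 2b follows study week = 48 + FU week: 48+2 = 50, 48+24 = 72, 48+48 = 96. All match. Table 2c follows 100 + Ext FU week: 102, 124, 148. With the latest permitted stop (FU W48), Ext FU Week 24 is 48+48+24 = 120. That matches SAP 3.1 and protocol 9.5 but not 124; in Table 2c, 120 belongs to Ext FU Week 20. The last label, 148, exceeds the longest possible study week, 48+96 = 144. Adding the 4-week screening phase (4+48+48+24) would give 124, but no other analysis week in the SAP counts screening.

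**Step 2: label error.** For a stop at FU week s, true study week = 48 + s + e and label = 100 + e, where e is the Ext FU week. Excess = 52 − s.

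**Step 3: which values are lost.** Stop day d = 7s + 1; extended day = FU day − d.

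| Stop visit | Stop day (FU) | Week 72 | Week 96 | Label excess (weeks) |
|---|---|---|---|---|
| FU W2–W20 | 15–141 | lost | lost | 50–32 |
| FU W24–W42 | 169–295 | kept | lost | 28–10 |
| FU W48 | 337 | kept | kept | 4 |

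The ±4-day visit window changes none of these: 141+4 = 145 < 156; 169−4 = 165 ≥ 156; 295+4 = 299 < 317; 337−4 = 333 ≥ 317.

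Example, stop at FU W12 (d = 85): the Week 72 target, FU day 169, becomes extended day 84, which falls in [72, 99] and is labelled Week 112. The Week 96 target, FU day 337, becomes extended day 252, which falls in [233, 274] and is labelled Week 136.

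**Step 4: Arm 6.** While on NA, Arm 6 is seen every 12 weeks, so a FU W12 lab leads to a stop at FU W24. Stops at FU W24 or W36 (days 169, 253) keep Week 72 (window from day 100) and lose Week 96 (window from day 275); a stop at FU W48 keeps both. Week 72 is lost only if a Week 48 lab leads to a stop at FU W12. The pattern of loss therefore differs from Arms 1–5.

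**Step 5: illustration only.** Suppose a proportion p = 25% of an arm truly has HBsAg <10 IU/mL at Week 72, and a proportion m of the arm is displaced, all of them among that 25%. With observed cases as denominator the result is (p − m)/(1 − m): 23.5% for m = 2%, 21.1% for 5%, 16.7% for 10%. With the whole arm as denominator it is p − m: 23%, 20%, 15%. The values of p and m are assumptions.

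**The case against.** The strongest reply is that the restarted axis is protocol design. The Schedule of Activities restarts at Ext FU W2 after NA stops, follow-up is extended by 48 weeks from that point, and these participants have their own endpoint: seroclearance 24 and 48 weeks after stopping. That stands. The gap is the missing second mapping for outputs defined at study weeks.

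A reader might infer that everyone with HBsAg <10 IU/mL disappears, or that data are thrown away. The documents do not support either reading. Someone below 10 IU/mL who fails another criterion, or who stops at Week 48, stays on the FU axis. Displaced values appear in listings and in the extended-phase rows of the threshold tables. Nor are the main results touched. The primary endpoint uses Week 44 labs; functional cure at Week 72 and Week 96 seroclearance require the stopping criteria to be met at Week 48; off-treatment endpoints run from the stop date; and time-to-event endpoints use dates.

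For the MMRM, the values that trigger the stop remain in the model, so an observed-case shift does not carry over directly to its estimates. That also stands as a limit on the bias claim, though the values at the weeks of interest are still absent.

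The Table 2c numbers might be sort codes, since the same column holds −1, 49 and 999. The text labels are indeed correct. But Table 2b in that column is a true study-week scale, and SAP 3.1 uses a study week for the same visit. The largest label error (50 weeks) needs a stop at FU W2, and hence a Week 48 lab that counts as qualifying; a FU W2 lab leads to a stop at FU W4 (48 weeks).

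**Conclusion.** The point holds for a defined set of outputs: the by-week marker summaries, thresholds, Week 72/96 cumulative plots and MMRM in SAP 5.4.5, and the over-time displays in 5.5.2. In Arms 1–5 a late completer who stops at FU W2–W20 has neither a Week 72 nor a Week 96 value there, and one who stops at FU W24–W42 has no Week 96 value. The loss is selective because response triggers it.

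The size of the bias cannot be stated, because the number and timing of late stops are not given. Its direction is downward for HBsAg control only if late completers hold their response at those weeks. The pattern assumes the last dose is taken on the stop visit. If it was taken the day before, that visit becomes extended Day 1, and stops at FU W24 and FU W48 also lose Week 72 and Week 96 respectively.

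The label conflict is certain: every Table 2c week exceeds the true study week by 52 minus the FU stop week, so by at least 4 weeks. The point should be corrected, but it does not threaten the primary or key secondary conclusions.

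**What to change.** Add a second analysis-week variable counted from FU Day 1 for all participants, whatever their NA status, through study Week 96. Use it for the by-week outputs in SAP 5.4.5 and, where a sample falls in the window, 5.5.2. Because the Week 96 window in Table 2b has no upper limit, state where it closes once extended visits can enter it. Keep the extended follow-up day for endpoints timed from stopping NA. Change Table 2c to 96 + Ext FU week, which agrees with SAP 3.1, or drop its study-week column. The 96 offset is exact only for a stop at FU W48, so dropping the column is cleaner.

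The cost is revised wording in SAP 2.1 and one derived variable, with no new data. Recovery will not be complete for HBcrAg, which has no sample between Ext FU W12 and W24. For a stop at FU W4 (day 29) those samples fall at FU days 29+85 = 114 and 29+169 = 198; for a stop at FU W8 (day 57), at 142 and 226. None lies in 156–190, so HBcrAg stays missing at Week 72 for such participants, and the SAP should say so.
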